3.7.2 Exclusions to Dose Limiting Toxicities

- Grade 3 infusion-related reaction resolving within 6 hours and controlled with medical management.
- Any Grade 3/4 non-hem toxicity that occurs in the first 10 days after RFA or TACE and which is an expected toxicity of the procedure in the opinion of the PI. These symptoms include, but are not limited to, fevers/rigors, pain, fatigue and nausea.
- Any grade 3 immune-mediated adverse event (including but not limited to Grade 3 diarrhea, Grade 3 skin toxicity, or Grade 3 liver enzyme elevation) that improves to \leq Grade 2 within 1 week of onset with supportive care (which may include systemic corticosteroids).
- Nausea and vomiting Grade 3 will only be considered dose-limiting if it is refractory to anti-emetic therapy and unable to be corrected to Grade 1 or less within 48 hours.

- Grade 3 rise in creatinine, not corrected to Grade 1 or less after 2 liters of intravenous fluids within 24 hours, will be considered dose limiting.
- Single laboratory values out of normal range that are unlikely related to trial treatment according to the investigator, do not have any clinical correlate, and resolve within 7 days with adequate medical management.
- Transient (≤ 24 hours) Grade 3 fatigue, local reactions, headache, nausea, emesis that resolves to \leq Grade 1.
- Grade 4 elevation in transaminase elevation that improves to \leq Grade 2 within 10 days of onset with supportive care.
- Grade 3 endocrinopathy that is managed with or without systemic corticosteroid therapy and/or hormone replacement therapy and the following criteria are met:
 - The subject's hormone levels are within normal limits
 - The subject is asymptomatic
- Grade 3 inflammatory reaction attributed to a local antitumor response (eg, inflammatory reaction at sites of metastatic disease, lymph nodes, etc.)

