3.3.2 Treatment

Three patients will be treated at 3.5mg/kg (with subsequent dosing also at 3.5mg/kg i.e. no inpatient dose escalation) prior to enrolling to the 10 mg/kg dose level. If a single patient experiences dose-limiting toxicity (DLT) related to the combination of TACE/RFA and

Tremelimumab this cohort will be expanded to N=6 as per a standard 3+3 design. If 3.5mg/kg is established to be safe we will proceed to the 10 mg/kg dose level. N=20 patients will be treated at 10 mg/kg to evaluate the feasibility endpoint, provided no more than 2 of 3-6 patients have a DLT at this level.

Dose level	Tremelimumab dose (mg/kg)	N
1	3.5	3-6
2	10	20

- The 3.5 mg/kg cohort will have at least 3 patients to evaluate for toxicity to establish MTD for the combination of Tremelimumab with either TACE or RFA. Three patients will be treated at this dose level. The descriptions and grading scales found in the revised NCI Common Terminology Criteria for Adverse Events (CTCAE) version 4.0 will be utilized for AE reporting. If none of the three patients at the 3.5 mg/kg dose level experiences dose-limiting toxicity (DLT), accrual to DL2 will proceed to the 10mg/kg cohort. If one of three patients treated at a dose level experiences DLT that is considered to be at least possibly related to the combination of Tremelimumab with either TACE or RFA, then three more patients will be enrolled at that same level. If the incidence of DLT among those six patients is one in six, then we will proceed to 10 mg/kg. If two or more of the six patients experience DLT, then the MTD is considered to have been exceeded.
- Evaluation period for Dose-limiting Toxicities (DLT) will extend for the first 8 weeks of the study.
- Following completion of the dose escalation portion of the study Tremelimumab will be administered at the MTD at the same schedule. A total of 20 patients will be treated in cohort A at the MTD, not including those patients treated at the lower doses.
- For patients on Dose Level 1 who have completed at least 16 weeks of protocol therapy, we will consider dose escalation to 10mg/kg if criteria for continuance of therapy are met and the patient does not have >Grade 2 toxicity attributable to tremelimumab.

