3.7 DOSE LIMITING TOXICITIES

3.7.1 Definition of Dose-limiting Toxicities (DLTs):

A DLT is defined as a \geq Grade 3 adverse drug reaction (ADR) according to the NCI-CTCAE v4.0, that is possibly, probably, or definitely related to the combination of Tremelimumab with either TACE or RFA, occurring during the DLT evaluation period except for any of the following outlined in section 3.6.2. ADRs are defined in this trial as any AEs suspected to be related to Tremelimumab by the investigator. Evaluation period for Dose-limiting Toxicities (DLT) will extend for the first 8 weeks of the study.

Treatment-related SAE will be ascribed as related to drug except where a clear relationship to the underlying disease or recognized co-morbidities is evident. For this trial, the MTD is defined as the highest dose where < 2 of 6 subjects experience a DLT.

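### Section 3.7.2 excuses a Grade 4 transaminase rise that recovers after 1 week but within 10 days, yet counts a Grade 3 rise with the same recovery time as a DLT

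*Combined protocol and SAP*

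**What the plan says.** Section 3.7.1 makes any Grade 3 or higher adverse drug reaction in the first 8 weeks a DLT if it is "possibly, probably, or definitely related to the combination of Tremelimumab with either TACE or RFA", unless section 3.7.2 excludes it. Two of those exclusions set recovery limits for liver enzymes.

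- Grade 3: "Any grade 3 immune-mediated adverse event (including but not limited to Grade 3 diarrhea, Grade 3 skin toxicity, or Grade 3 liver enzyme elevation") is excluded only if it falls to Grade 2 or lower within 1 week of onset.
- Grade 4: a "Grade 4 elevation in transaminase elevation that improves to" Grade 2 or lower within 10 days of onset is excluded. This bullet does not require the event to be immune-mediated.

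A further bullet treats Grades 3 and 4 alike. It excludes "non-hem toxicity that occurs in the first 10 days after RFA or TACE and which is an expected toxicity of the procedure" in the PI's opinion.

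The DLT count feeds these rules:

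- Section 3.7.1: "the MTD is defined as the highest dose where < 2 of 6 subjects experience a DLT".
- Section 3.3.2, for 3.5 mg/kg: "If two or more of the six patients experience DLT, then the MTD is considered to have been exceeded".
- Section 3.3.2, for 10 mg/kg: 20 patients are treated "provided no more than 2 of 3-6 patients have a DLT at this level".
- Section 8.1, for 10 mg/kg: accrual stops at two or more DLTs among the first 3-6 patients.

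**The concern.** A DLT rule should not treat a worse event more leniently than a milder one of the same kind and duration. Here the longer allowance belongs to the higher grade, and the text gives no reason for it.

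The toxicity is an expected one. Section 1.2.4.2 reports that 5 of the Grade 3 or higher events in an earlier tremelimumab study of 21 HCC patients were raised transaminases, against one pruritus and one purpura. Section 3.9.3 lists hepatitis among the most common severe immune-mediated reactions.

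At stake is how the DLT counts at 3.5 and 10 mg/kg are read. So is the statement in section 3.6, on which Cohorts D and E rely, that the 10 mg/kg schedule was shown to be safe and feasible in Cohort A. With three to six patients per decision, one reclassified event can matter.

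**Working it through.** The plan states no figure on this point, so the check applies the rules to each case and then illustrates the sensitivity.

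**1. Classification.** Take a related transaminase rise in the 8-week window, outside the post-procedure exemption.

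| Time from onset to Grade 2 or lower | Grade 3, immune-mediated | Grade 3, not immune-mediated | Grade 4, any mechanism |
|---|---|---|---|
| Within 1 week | not DLT | DLT | not DLT |
| After 1 week, within 10 days | DLT | DLT | not DLT |
| After 10 days | DLT | DLT | DLT |

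The middle row is inverted. The first row is inverted too for a Grade 3 rise that is not immune-mediated.

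**2. Boundary.** If onset is day 1, day 8 is 7 days later and may count as within 1 week. Days 9 and 10 are inverted on either count.

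**3. Other bullets in 3.7.2.** The single-laboratory-value bullet needs a value unlikely to be related that resolves within 7 days, so it cannot rescue a related rise lasting longer. The bullet on a Grade 3 inflammatory reaction to local antitumor response has no time limit, and some Grade 3 rises might be argued into it, but it does not name transaminases. The remaining bullets concern other toxicities.

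**4. Calendar time outside the post-procedure exemption.** Section 3.7.1 ties a DLT to the combination but also says that "ADRs are defined in this trial as any AEs suspected to be related to Tremelimumab by the investigator".

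- If tremelimumab-only reactions count: 56 − 10 = 46 days, or 56 − 11 = 45 if the procedure day is added.
- If the procedure must have taken place on Day 36: days 36-56 are 21 days, leaving 11 or 10.
- At the edges of the ±96-hour window: Day 32 leaves 25 − 10 = 15 or 25 − 11 = 14; Day 40 leaves 17 − 10 = 7 or 17 − 11 = 6.

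These are days, not risks.

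**5. Illustration.** Assume one Grade 4 event that is excused now and would count under a 1-week limit. Assume the other patients have independent DLT probability p (an assumption; the documents give none).

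- 3.5 mg/kg, no other DLT in the first three: 0/3 becomes 1/3 and three more patients are treated. P(MTD exceeded) = 1 − (1 − p)³.
- 10 mg/kg, six assessed, section 8.1 (stop at two or more): the event is decisive if exactly one of the other five has a DLT, 5p(1 − p)⁴.
- 10 mg/kg, six assessed, section 3.3.2 (up to two allowed): decisive if exactly two of the other five do, 10p²(1 − p)³.

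| p | 3.5 mg/kg | 10 mg/kg, section 8.1 | 10 mg/kg, section 3.3.2 |
|---|---|---|---|
| 0.10 | 0.271 | 0.328 | 0.073 |
| 0.20 | 0.488 | 0.410 | 0.205 |
| 0.30 | 0.657 | 0.360 | 0.309 |

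None of these allows for the separate halt in section 3.3.3 at two attributable Grade 4 events.

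**The case against.** The strongest reply is that nothing live turns on this. Section 8.1 says feasibility was settled before amendment G and that efficacy is now primary. Section 3.6 gives Cohorts D and E no dose escalation and places them under the stopping rules, which act on grade and attribution with no recovery exemption. The rationale in section 8.2 for those cohorts rests on 9/10 patients meeting the feasibility goal, not on DLT counts.

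A Grade 4 rise is also caught elsewhere. Section 3.9.2 ends tremelimumab for a drug-related Grade 3 or higher laboratory abnormality. With four-weekly dosing the third dose falls on day 57, so an evaluable patient stopped inside the window would count against the three-dose feasibility endpoint. Section 7.5.1 bases escalation on toxicity data from prior patients, and sections 7.2.2 and 8.3 tabulate grades.

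Most of this stands and limits the consequence. It does not change DLT status, and neither table is said to show recovery time or which exclusion was applied. Section 2.1.3.2 also makes a related DLT a bar to re-induction, but it bars patients taken off for toxicity as well, so I put little weight on that route.

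A reader might infer that escalation to 10 mg/kg was wrong, or that the percentages above estimate how often a decision was distorted. The documents support neither. They report no DLT counts, no Grade 4 transaminase event in this trial, and no frequency of recovery between 1 week and 10 days.

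**Conclusion.** The inversion is real on the literal text: certain for recovery on days 9 and 10, dependent on day-counting for day 8, and open to argument for Grade 3 rises that could be attributed to local antitumor response. It is wider than the two time limits, because the Grade 3 exemption requires an immune-mediated event and the Grade 4 exemption does not.

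Its practical size is unknown. The probabilities of 27% to 66% at 3.5 mg/kg, and of 33% to 41% (section 8.1) or 7% to 31% (section 3.3.2) at 10 mg/kg, are conditional on one qualifying Grade 4 event, on assumed DLT rates of 10% to 30%, and on tightening the Grade 4 rule. They show that a single reclassification could matter in groups this small, not that one did. No pending escalation decision changes. The effect is on the reported DLT counts and on the safety statement for 10 mg/kg, and it should be corrected.

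**What to change.** Make the Grade 4 transaminase exemption no broader than the Grade 3 one, with the same 1-week limit and the same immune-mediated condition, or delete it. Aligning the time limits alone is not enough: a related Grade 3 rise that is not immune-mediated would remain a DLT while a comparable Grade 4 rise was excused. Setting both limits at 10 days has that same gap and could only lower the count.

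From recorded laboratory data, list each Grade 3-4 transaminase event in the 8-week window with peak grade, attribution, onset relative to the procedure, days to Grade 2 or lower, and any exclusion used. State how day 1 of onset is counted. Tabulate DLTs at 3.5 and 10 mg/kg under the current and corrected rules, and say whether any 3+3 or accrual call would have differed.

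The cost is one edited bullet and a short listing. Recovery can be dated only as closely as blood was drawn; section 3.9.3.2 asks for more frequent liver tests but sets no interval, so some dates may be bounds. The DLT count can only stay the same or rise, so the safety summary may look slightly less favourable.

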3.8 DRUG ADMINISTRATION

3.8.1 Tremelimumab Drug Administration

The first day of dosing is considered Day 1. Each dose of investigational product should be administered using the following guidelines:

- 1) Investigational product must be administered at room temperature (25°C) by controlled infusion at a rate of 250 mL/hr via an infusion pump into a peripheral vein. Prior to the start of the infusion, ensure that the bag contents are at room temperature to avoid an infusion reaction due to the administration of the solution at low temperatures.
- 2) Investigational product must **not** be administered via IV push or bolus but as a slow IV infusion. The entire content of each IV bag will be infused using an infusion pump.
- 3) The infusion lines should be attached only at time of use. Lines used for infusion during dose administration will need to be equipped with 0.22 or 0.2 μ m in-line filters.
- 4) If there are no requirements to slow, interrupt, or permanently stop the infusion, the anticipated infusion time to deliver each dose (250 mL) is anticipated to be approximately 60 minutes.

The duration of the investigational product administration will be recorded.

3.8.2 Monitoring of Dose Administration

Vital signs will be collected before investigational product infusion and at the completion of the infusion.

As with any antibody, allergic reactions to dose administration are possible. Therefore, appropriate drugs and medical equipment to treat acute anaphylactic reactions must be immediately available, and study personnel must be trained to recognize and treat anaphylaxis, as per local institutional guidelines.

3.9 DOSING DELAYS

The following broad guidelines for dose delays apply to both of the planned dosages of Tremelimumab and are dependent on the clinical and laboratory assessment on the day of dosing. No dose reductions will be employed. Patients will either proceed or forgo treatment. Dosing may be delayed up to 14 days to allow recovery from treatment-related toxicity. For specific immune-mediated adverse reactions see Section 3.8.3 which will take precedence over this broad management guideline.

Condition	Management
Onset of any toxicity	Rule out alternative etiology In case of doubt, investigator should consult with study medical monitor promptly
NCI CTCAE Grade 1	Provide symptomatic treatment Possible topical steroids if applicable
NCI CTCAE Grade 2	Provide symptomatic treatment In the case of an immune-mediated adverse event do not give scheduled dose; dosing may be resumed once symptoms are resolved. Consider oral or IV steroids at the onset of symptoms. Taper steroid if symptoms improve.
NCI CTCAE Grade 3	Start high-dose IV steroids at the onset of the symptoms Provide symptomatic treatment
NCI CTCAE Grade 4	Start high-dose IV steroids at the onset of the symptoms Provide symptomatic treatment Permanent discontinuation ^a of Tremelimumab for all NCI CTCAE Grade 4 events (unless specific exemption stated elsewhere in protocol)
Steroid refractory toxicity (no improvement after 5 days on high-dose IV steroids) or relapse after reducing high-dose steroids	Continue symptomatic treatment and steroids Possible infliximab ^b 5 mg/kg IV for GI toxicities unless contraindicated [consult with GI specialist]. Caution: rule out bowel perforation and refer to label before using infliximab For subjects with increased AST/ALT, or total bilirubin levels, consider mycophenolate mofetil

ALT = alanine transaminase; AST = aspartate transaminase; GI = gastrointestinal; IV = intravenous; NCI CTCAE = National Cancer Institute Common Terminology Criteria for Adverse Events.

a Subjects will not receive any subsequent dose, but will remain on study and follow the other procedures required from the study (e.g., follow-up procedures, disease assessment scans, blood sample collections).

b Use will result in discontinuation of treatment.

During the study, subjects may require immunosuppressive medications such as steroids for management of underlying disease, treatment-related toxicity, or unrelated conditions. If symptoms resolved to NCI CTCAE Grade ≤ 1 , Tremelimumab dosing may be resumed during steroid taper. Subjects with adrenal insufficiency may take daily prednisone or equivalent therapy for their endocrinopathy while receiving Tremelimumab treatment. Topical and inhaled steroids in standard doses are allowed.

3.9.1 Dosing Delays/Dose Modifications: General Guidelines

3.9.1.1 Grade 1 or 2 Toxicity

Treatment with Tremelimumab need not be interrupted, although for chronic low grade toxicity causing significant detrimental effect in patient's well-being the PI may elect to delay/omit dosing at his discretion, in particular in the case of a suspected immune-mediated adverse event.

3.9.1.2 Grade 3 Hematologic or Non-Hematologic Toxicity

Hold Tremelimumab and re-evaluate until toxicity improves to \leq grade 1 or pre-treatment baseline. Treatment will be discontinued in patients who experience grade 3 non-hematologic toxicities felt to be drug-related.

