3.9.2 Toxicities Mandating Permanent Discontinuation of Tremelimumab

As per the Investigator's brochure the following criteria will result in permanent discontinuation of tremelimumab.

Condition	Action
CTCAE Grade ≥ 3 related diarrhea or colitis	Permanent discontinuation of tremelimumab for all listed conditions
AST or ALT $> 8 \times$ ULN or total bilirubin $> 5 \times$ ULN	
CTCAE Grade ≥ 3 hypersensitivity reaction or infusion reaction; Recurrent/persistent CTCAE Grade 2 hypersensitivity	
CTCAE Grade ≥ 3 endocrine disorders, if symptomatic and not controlled with hormone replacement therapy. (Tremelimumab may be dosed for CTCAE Grade ≤ 3 endocrine disorders, if asymptomatic and controlled with hormone replacement therapy.)	
CTCAE Grade 4 rash or other skin disorders (with the exception of vitiligo, which may be dosed regardless of severity)	
Any other CTCAE Grade ≥ 3 events thought to be drug-related	
Any CTCAE Grade ≥ 3 laboratory abnormalities thought to be drug-related	
Patient receives infliximab or any other TNF- α inhibitor	
2 consecutive doses missed due to on-going related toxicities	
Patient begins new investigational therapy, chemotherapy, cytokine therapy, or immunotherapy (including vaccines)	
Patient becomes pregnant	

ALT Alanine transaminase; AST Aspartate aminotransferase; CTCAE Common Terminology Criteria for Adverse Events; TNF Tumor necrosis factor; ULN Upper limit of the normal range.

[figure not shown]

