3.9.3 Specific immune-mediated adverse reactions

Tremelimumab can result in severe and fatal immune-mediated adverse reactions due to T-cell activation and proliferation. These immune-mediated reactions may involve any organ system, however, the most common severe immune-mediated adverse reactions are enterocolitis, hepatitis, dermatitis (including toxic epidermal necrolysis), neuropathy, and endocrinopathy. The majority of these immune-mediated reactions initially manifest during treatment, however, a minority may occur weeks to months after discontinuation of Tremelimumab. Tremelimumab will be discontinued and systemic high-dose corticosteroid therapy initiated for severe immune-mediated reactions.

Patients will be assessed for signs and symptoms of enterocolitis, dermatitis, neuropathy and endocrinopathy and evaluate clinical chemistries including liver function tests and thyroid function tests at baseline and before each dose.

The following are anticipated immune-mediated adverse reactions for which specific guidance and management is outlined below.

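### Hold or stop: 3.9.1.2 conflicts with 3.9.2 for drug-related Grade 3 haematologic toxicity, and 3.9.3.2 conflicts with 3.9.2 for severe liver test elevations

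*Combined protocol and SAP*

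**What the plan says.** Section 3.9.1, titled as general guidelines, contains 3.9.1.2, whose heading names both haematologic and non-haematologic Grade 3 toxicity. Its first instruction covers both: "Hold Tremelimumab and re-evaluate until toxicity improves to" Grade 1 or the pre-treatment baseline. Its second covers only one: "Treatment will be discontinued in patients who experience grade 3 non-hematologic toxicities felt to be drug-related".

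Section 3.9.2 is titled as a list of toxicities that mandate permanent discontinuation. Citing the Investigator's brochure, it says that "the following criteria will result in permanent discontinuation of tremelimumab". Three rows matter here:
- AST or ALT above 8 × ULN, or total bilirubin above 5 × ULN;
- any other Grade 3 or higher "events thought to be drug-related";
- any Grade 3 or higher "laboratory abnormalities thought to be drug-related".

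Section 3.9.3 covers immune-mediated reactions. It opens by saying that "These immune-mediated reactions may involve any organ system" and that "Tremelimumab will be discontinued and systemic high-dose corticosteroid therapy initiated for severe immune-mediated reactions". The severe row of its liver table (3.9.3.2) nevertheless says to hold when AST or ALT exceeds 5 × ULN or bilirubin exceeds 3 × ULN. It discontinues only if Grade 3 non-haematologic toxicity has not resolved to Grade 1 or baseline within 4 weeks.

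The only ranking sentence is in 3.9. It refers the reader to the section on specific immune-mediated reactions, "which will take precedence over this broad management guideline". It cites that section as 3.8.3; the section is now 3.9.3. It does not mention 3.9.2.

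**The concern.** These are dosing safety rules, and an investigator will look them up by type of event. Someone managing a Grade 3 cytopenia finds 3.9.1.2, whose title fits exactly. It gives a self-contained instruction and no pointer to 3.9.2. Someone managing severe immune-mediated hepatitis finds a hold rule in the section that 3.9 has just ranked highest. In both cases the patient could be given the antibody again after an event for which 3.9.2 requires a permanent stop.

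The choice also carries forward. Section 2.1.3.2 bars from re-induction patients who were taken off treatment for toxicity, so the reading adopted can decide later eligibility as well.

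**Working it through.** The documents give no figure to reproduce, and the point depends on no calculation. The check is a comparison of texts.

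**Case 1: Grade 3 haematologic toxicity thought drug-related**
- 3.9.1.2, first sentence: hold until recovery.
- 3.9.1.2, second sentence: discontinuation is limited to non-haematologic toxicity, so this event is not covered.
- 3.9.2: the other-events row or the laboratory row applies, so stop permanently. Other rows carry express exceptions (vitiligo, controlled endocrine disorders); neither of these does.

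Does 3.9.1.2 really imply re-dosing? It never says to resume. But if its hold were meant only for unrelated events, the qualifier excluding haematologic toxicity from the second sentence would do no work. Two other places fit the hold-then-resume reading. The 3.9 table orders permanent discontinuation in its Grade 4 row but not in its Grade 3 row. Section 3.12.1 removes patients whose slow recovery prevents re-treatment within 28 days, so it expects some re-treatment after toxicity.

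**Case 2: severe liver test elevation**

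| Level | 3.9.3.2 | 3.9.2 liver row |
|---|---|---|
| AST/ALT >5 to 8 × ULN, or bilirubin >3 to 5 × ULN | Hold; stop if unresolved within 4 weeks | Not reached |
| AST/ALT >8 × ULN, or bilirubin >5 × ULN | Same hold (no upper bound) | Permanent stop |

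The second line is the conflict, for a patient who recovers within 4 weeks. As in Case 1, the severe row implies resumption and does not state it. The opening of 3.9.3, which discontinues severe reactions, points towards stopping; the liver table beneath it does not.

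**Does any sentence rank the sections?** The ranking sentence in 3.9 sets the immune-mediated section above the broad guideline. It says nothing about 3.9.2 against 3.9.1, which leaves Case 1 open. It also does not say whether the priority of 3.9.3 extends over 3.9.2, which leaves Case 2 open.

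**How often?** The documents give no frequency for either case.
- Haematologic: 1.2.4.1 and 1.2.4.2 name no cytopenia. Entry is allowed from 60,000/mcL platelets and 1,000/mcL neutrophils (2.1.1.8), so the event is plausible.
- Liver: 1.2.4.2 reports 5 cases of Grade 3 or higher transaminase elevation among 21 patients with HCC given a different schedule. If each case was a different patient, that is 5/21 = 24%. How many exceeded 8 × ULN is not stated, so the share in dispute could be anywhere from 0% to 24%, before removing those who did not recover in time.

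**The case against.** The best reply is that the sections do not give incompatible orders. Section 3.9.1.2 authorises no re-dosing; the conflict rests on an inference from one qualifier. Section 3.9.2 is express and unconditional, and its title is mandatory where that of 3.9.1 is general. The hold can still serve events not thought drug-related, which leaves a redundant word and loose drafting. An investigator who discontinues breaches neither section. Even under the hold reading there are other exits: the 14-day delay limit in 3.9, the 28-day limit in 3.12.1, and two consecutive missed doses in 3.9.2.

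Most of this stands. Re-dosing is implied only, 3.9.2 is probably meant to govern, and the group affected is small. What does not stand is that the documents settle the matter. The priority of 3.9.2 has to be inferred from titles, while the one sentence that does rank sections leaves it out.

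Two further inferences are tempting. One is that the protocol instructs investigators to re-dose after these events; neither 3.9.1.2 nor the severe liver row says so. The other is that the opening of 3.9.3 settles all severe immune-mediated reactions, leaving only haematologic events in doubt; the severe liver row shows that it does not.

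**Conclusion.** Wrong as written: the dosing rule is internally inconsistent in two places. Severity is low. The first place is confined to Grade 3 haematologic events thought drug-related. The second is confined to AST or ALT above 8 × ULN, or bilirubin above 5 × ULN, with recovery within 4 weeks. Few patients are likely to be affected, but that is a judgement: the documents name no cytopenia and do not say how many liver elevations exceed the 3.9.2 thresholds. The liver case has the more direct support, because Grade 3 or higher transaminase elevations were reported in HCC.

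The conclusion assumes that the qualifier in 3.9.1.2 was meant to have effect, and that a hold pending recovery contemplates resumption. A reader might go further and infer that patients were re-dosed against the brochure, or that the feasibility or efficacy results are affected. The documents contain nothing on either.

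**What to change.** Make three wording edits in one amendment:
1. State that 3.9.2 governs over 3.9.1.
2. Amend 3.9.1.2 so that drug-related Grade 3 haematologic events are also discontinued, and the hold applies only to events not thought drug-related.
3. State that the liver thresholds in 3.9.2 override the hold in 3.9.3.2, so that the hold runs only up to 8 × ULN for AST or ALT and 5 × ULN for bilirubin. The same sentence should say that the liver row of 3.9.2, not its general laboratory row, sets this limit. The severe row itself refers to Grade 3 toxicity, and the general row could otherwise be read to leave the hold nothing to cover.

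Optionally, make the general sentence in 3.9 on resuming during steroid taper subject to 3.9.2. Correcting the stale 3.8.3 reference to 3.9.3 would be sensible at the same time.

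The edits need no extra visits, patients or data. The downside is that a few patients who might have been re-dosed after recovery lose further doses, which 3.9.2 already requires.
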